Cover Page

Official Title of the Study: Teleoperation Experimental Comparison With Able-bodied Subjects

Document Date: July 19, 2022

NCT Number: NCT05048394

COMIRB Protocol

COLORADO MULTIPLE INSTITUTIONAL
REVIEW BOARD
[name] [contact] [contact]

Protocol #: 14-0838

Project Title: Biomechatronics Development Lab Myoelectric Controller protocol

Principal Investigator: [name]

Version Date: 07/19/22

I. Hypotheses and Specific Aims: The purpose of this protocol is to provide guidelines for research and development of more intuitively controlled myoelectric prosthesis. Self-identified adult volunteers will be used for convenience sampling for the population served.

II. Background and Significance: Currently available multi-joint prostheses cannot be fully utilized because there are fewer control inputs than the number of joints that need to be controlled. Based on the work in the field of neuroscience, it has been shown that grasping is a 'low dimensional' task (i.e. – only 2-3 control inputs are necessary). We will develop control paradigms and upper limb prostheses components to control a multi-joint prosthetic hand using currently available clinical practices and investigate which dimensions are most important for prosthetic devices.

III. Preliminary

Studies/Progress Report:

IV. Research Methods

A. Outcome Measure(s):

Outcome measures include completion rate, time to completion and path efficiency metrics as well as position of the arm, wrist, and hand during these tasks.

Additional outcome measures may include time of use, types of actions performed, location information (GPS), and/or power consumption. These metrics help define the performance of the postural control paradigm for EMG control and design of advanced prosthetic hands.

B. Description of Population to be Enrolled:

The subject population will consist of a convenient sample of adult volunteers, both able bodied and limb deficient. The subjects will have various ethnicity, age, and gender. An estimated total of 60 subjects will be enrolled. The subjects must be able to understand and follow directions in English, assessed by their ability to respond during the recruitment and consent process. Exclusion criteria include any subjects that are not able to understand the procedures or are taking blood thinners. Subjects will be recruited via flyers placed at the Anschutz or Auraria campuses, flyers emailed to organizations that work with our target population, or in-person at conferences and events to which we have been invited.

Because of the potentially long distances we will need to travel to meet with participants and the demands of work on other researchers we will not be able to have more than one researcher travel at a time. In order to ensure the safety of a single researcher traveling to a participant's location, we will enforce the following safety procedures:

When traveling to off-site locations, researchers only a licensed and insured driver in a well-maintained vehicle with appropriate equipment for conditions will drive. Driver has AAA membership which will be used in case of emergency. Experimentation will only take place during normal business hours when other research staff can be reached in case of unanticipated emergency.

We will keep a log in the lab describing where we are traveling and with whom we are meeting. We will only travel to participants with whom we have previous contact and have determined to be safe. Traveling researcher will keep a cell phone with them and check in with other researchers in the lab at least every 3 hours via cell phone to confirm that they are safe.

C. Study Design and Research Methods

The experiments will take place at the Biomechatronics Development Laboratory in the Children's Hospital on Anschutz campus, the University of Boulder Campus, and/or during normal at-home use. The participant will come up to 3 times for up to 4 hour sessions. An optional at-home use period can take place for up to 6 months. During this session the participant will be asked to control a virtual hand (a 3D image of a hand on the computer screen) and/or a prosthesis by contracting the muscles in the forearm and to manipulate physical objects on the table. The only devices coming into contact with the participant will be standard of care myoelectric control and motion capture equipment including surface and intramuscular electromyographic (EMG) sensors. Other equipment to be used in the laboratory include a data glove (Cyberglove II by Cyberglove Systems, LLC), vibrating motors, reflective markers (OptoTrak, Northern Digital Inc), and electrogoniometers (Biometrics Goniometer, Motion Lab Systems, Inc.). During at-home use, subjects will use standard of care surface EMG sensors installed into a prosthetic socket. Standard of care procedures involving palpation of the subject's arm will be used to locate the best position on the arm for the surface and Intramuscular EMG and motion capture sensors. The EMG sensors measure muscle activation levels and send the information to the computer to enable the control of the virtual hand or prosthesis. The motion capture sensors and goniometers give us a measurement of the position of the arm. A training period will be followed by several tests to measure the intuitiveness and functionality of several versions of the controller. Different versions of the controller will be presented to the subject in a randomized order. The subject will be expected to try and acquire target hand postures displayed on the screen using this control interface. Subjects will likewise be given a training period to practice moving the physical objects.

Additionally, we may travel to the subject's preferred location (*e.g.* home or office) to conduct testing with surface EMG, motion capture, goniometers, or video. This will allow us to maximize recruitment and include subjects who live too far from the Anschutz campus to participate.

Video will be taken from behind and will not include identifying information such as the subject's face. Video will be used to record arm and shoulder motion during the experiment to be analyzed later. This allows us to determine whether compensatory motion is affected by different prostheses.

An optional home-use period may take place. A prosthetic limb system using surface EMG sensors and a prosthetic hand will be sent home with the subject. It will be used during everyday activities. The surface EMG sensor will be permanently installed into the prosthetic limb system and will not need to be replaced. The subject will be asked to use the prosthetic limb system as their primary prosthetic limb (daily use) unless it is not appropriate due to the task/environment. The home-use period will last up to 6 months.

D. Description, Risks and Justification of Procedures and Data Collection Tools:

We will be acquiring muscle activity data for the control of a prosthesis using Electromyography (EMG) in conjunction with motion capturing devices and finger mounted force sensors. Surface EMG allows us to create pattern recognition of a composite muscle signal, and intramuscular EMG allows us to focus on particular muscles, or muscle slips. Risks of Surface EMG and motion capture are possible minor skin discomfort from the medical tape/adhesive used to attach sensors to the skin and/or from preparation of skin for attachment. The intramuscular EMG electrodes introduce a minimal risk of infection, and nerve injury as well as minimal bleeding. Any injury to nerves is temporary and may involve numbness or pain. When the procedure is finished, the electrodes will be removed. All equipment and insertion sites will be sterilized in accordance to standard of care procedures. The Intramuscular EMG electrodes may be used in conjunction with surface EMG or as an alternative to surface EMG. If you feel that you have been harmed while participating in this study, you should inform [name] at [contact] immediately.

E. Potential Scientific Problems:

Potential scientific problems include a lack of subjects with upper-limb amputation and the inability of subjects to learn the postural control paradigm to a high level.

F. Data Analysis Plan:

Data will be processed with standard techniques in MATLAB (Mathworks, Inc.) in order to produce the metrics described previously (completion rate, time to completion, and path efficiency).

G. Summarize Knowledge to be Gained:

The development of more intuitive and functional prosthesis controllers will augment the quality of life for people with upper-limb amputation.

H. References:

N/A

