#### Evaluating the efficacy of the *Semi-Autonomous Myoelectric Control Algorithm*:

**Hypothesis 1 (primary):** We hypothesize that use of *Semi-Autonomous Myoelectric Control Algorithm* will improve dexterity relative to the standard-of-care prosthetic treatment. To validate this hypothesis, we will compare the two treatments (Treatment 1 vs. 2) during a single laboratory-based session using a task involving the transfer of a fragile object, recording the transfer success rate. We will use an Anderson-Darling test to check for normality. If the sample is normally distributed, we will use a two-sample Student's t-test to compare Treatment 1 and 2. If the sample is not normally distributed, we will use a Wilcoxon Rank Sum test to compare Treatment 1 and 2. If the hypothesis is correct, then we expect Treatment 1 (the *Semi-Autonomous Myoelectric Control Algorithm*) to show a significantly higher transfer success rate than Treatment 2.

**Hypothesis 2 (secondary):** We hypothesize that use of *Semi-Autonomous Myoelectric Control* will also provide improved assistance with prolonged gross motor movements. To validate this hypothesis, we will compare the two treatments (Treatment 1 vs. 2) during a single laboratory-based session using a task involving holding an object in the air for 2 minutes and recording the number of times the object is dropped. We will use an Anderson-Darling test to check for normality. If the sample is normally distributed, we will use a two-sample Student's t-test to compare Treatment 1 and 2. If the sample is not normally distributed, we will use a Wilcoxon Rank Sum test to compare Treatment 1 and 2. If the hypothesis is correct, then we expect Treatment 1 (the *Semi-Autonomous Myoelectric Control Algorithm*) to show a significantly fewer drops than Treatment 2.

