### Power Calculation

Power was calculated using the 'sampsizepwr' package in MATLAB (version 2018a). The primary outcome measure, transfer success rate of the fragile object, was used to inform the power calculation. We used an average success rate of  $59.2\% \pm 20.7\%$  from [1]. We selected a z-test for normally distributed data with a known standard deviation to derive the number of subjects necessary to detect a 20% difference in success with 80% power. The result of this calculation indicated that a sample size of 9 subjects will achieve a power greater than 80%.

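### If each subject uses both controllers, the plan leaves order balance unspecified and tests without a subject or period term; a blocked order list and a crossover analysis would be a cheap improvement

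*Protocol*

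**What the plan says.** Protocol IV.C (Study Design and Research Methods) states "Different versions of the controller will be presented to the subject in a randomized order". It gives no generation method, blocking or balancing rule, and describes no rest or washout between controllers. On practice, it says "A training period will be followed by several tests to measure the intuitiveness and functionality of several versions of the controller" and, for the object tasks, "Subjects will likewise be given a training period to practice moving the physical objects". Neither training period has a stated length or performance criterion. On session length it says "The participant will come up to 3 times for up to 4 hour sessions".

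For the primary hypothesis the SAP says "we will compare the two treatments (Treatment 1 vs. 2) during a single laboratory-based session using a task involving the transfer of a fragile object". The secondary hypothesis uses a task of "holding an object in the air for 2 minutes and recording the number of times the object is dropped". For both, the test is a two-sample Student's t-test if the data pass an Anderson-Darling check, and otherwise a Wilcoxon rank sum test. Neither test has a term for subject, order or period.

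The SAP's Power Calculation takes a success rate of 59.2% with SD 20.7%, a 20% difference and a z-test, and concludes that "a sample size of 9 subjects will achieve a power greater than 80" percent.

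**The concern.** When one person uses two controllers in one session, the second may be used with more skill or with a more tired arm than the first. The documents make this plausible but do not measure it. Protocol IV.E lists "the inability of subjects to learn the postural control paradigm to a high level" as a scientific problem, control is by forearm contraction, sessions can be long, and the secondary task is a sustained hold.

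Randomising the order protects against systematic bias. It does not remove the order effect from the data of one small trial. If the two orders are unequally represented, part of the first-versus-second difference sits in the treatment estimate. Even when they are nearly equal, the order effect stays in the error term unless the analysis takes it out. At 9 subjects there is little precision to spare for the primary comparison, and replacing the unpaired test with a plain paired one would not cure this.

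**Working it through.** **Inputs from the documents.** 9 subjects, SD 20.7 points and a 20-point target difference (SAP, Power Calculation); two treatments (SAP, Hypotheses 1 and 2).

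**Assumptions not in the documents.** Two-sided 5% level; each subject uses both controllers; simple (coin-toss) randomisation of order; an additive second-minus-first effect π of 0 to 20 points; 20.7 reused as the SD of within-subject differences; no differential carryover.

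**1. The plan's own figure.** One-sample z-test: n = [20.7 × (1.960 + 0.842) / 20]² = 8.41, rounded up to 9, with power 82.6% at n = 9. The stated figure reproduces. With the SD estimated, a paired t-test at n = 9 has 72% power.

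**2. Chance of an uneven order.** Under Binomial(9, 0.5):
- 6:3 or worse: 260/512 = 50.8%
- 7:2 or worse: 92/512 = 18.0%

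Because 9 is odd, 5:4 is the best balance available.

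**3. Effect on the estimate.** With n₁ and n₂ subjects in the two orders and no period term, the realised shift is π × (n₁ − n₂)/9. For π = 10 this is 1.1 points at 5:4, 3.3 at 6:3 and 5.6 at 7:2. For π = 20 it is 2.2, 6.7 and 11.1. Averaged over all splits, the shift is zero.

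**4. Effect on precision.** Under simple randomisation the SE of the mean difference is √(20.7² + π²)/3, which is 6.9, 7.7 and 9.6 for π = 0, 10 and 20. With a 5:4 list and the larger sequence chosen at random, it is √(20.7²/9 + (π/9)²), which is 6.9, 7.0 and 7.2. With a period term as well, it is 20.7 × √[(1/5 + 1/4)/4] = 20.7 × √0.1125 = 6.9 whatever π is. Without the period term or any order effect the variance factor is 1/9 = 0.1111, so the term costs about 1% of variance.

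**5. Power for a 20-point difference** (simulation, 100,000 or more runs per cell). The last row assumes SD 20.7 under each treatment and within-subject correlation 0.5.

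| Analysis | π = 0 | π = 10 | π = 15 | π = 20 |
|---|---|---|---|---|
| Paired t, simple random order, order ignored | 72% | 63% | 53% | 43% |
| 5:4 order with period term | 70% | 70% | 70% | 70% |
| Planned two-sample t on the same 9 subjects | 49% | 46% | 43% | 40% |

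The type I error of the first row stays near 5% when averaged over splits.

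**6. Which between-sequence test.** Let δ be the Treatment 1 minus Treatment 2 effect. Subjects given Treatment 1 first have mean first-minus-second difference δ − π; those given Treatment 2 first have −δ − π. The contrast between sequences is 2δ, so π cancels and half the contrast is the treatment estimate. Treatment 1 minus Treatment 2 differences have means δ − π and δ + π; their contrast between sequences is 2π in size, which is the period effect. In simulation that second test rejects 5% of the time with a true 20-point benefit and no order effect, and 46% of the time with a 15-point order effect.

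No power figure is given for the drop count in Hypothesis 2, because the documents supply no variance for it.

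**The case against.** - **Bias.** A reader might infer that the plan biases the comparison or inflates false positives. It does not: randomised order gives zero expected bias from an additive order effect. At a 7:2 split with most subjects taking Treatment 1 second, a 15-point order effect would raise false positives in its favour to about 11% against 2.5%. But a 7:2 or worse split in that direction occurs in only 46/512 = 9% of trials, and the opposite split is equally likely.
- **Balancing.** A reader might also infer that the orders are not balanced. The protocol neither states nor excludes balancing; it is unspecified.
- **Design.** The within-subject reading is not certain. The protocol sentence concerns several controller versions in a general laboratory protocol. The SAP's Data Analysis section speaks of two groups, and its two-sample tests would suit parallel groups, where order does not arise. An earlier part of the SAP was not available for this review and may settle this. The recommendation must therefore be conditional.
- **Training.** Practice on the physical objects should reduce learning during the transfer task. It has no stated length or criterion, and it does not address fatigue.
- **Size under the planned test.** With the unpaired test, order effects of 10 to 20 points cost only about 3 to 9 points of power. Ignoring the pairing costs more: 49% against 72% at correlation 0.5. That stands. But once the pairing is used, order becomes the next avoidable loss, so both belong in one correction.

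**Conclusion.** The point holds conditionally and is a cheap improvement, not a flaw that invalidates the comparison. If each subject uses both controllers, the order-generation method is missing and the named tests cannot remove an order effect. What is at stake is precision and chance imbalance. Against a paired test that ignores order, a 5:4 list with a period term gains about 7 points of power at an order effect of 10 (70% against 63%) and about 27 at 20 (70% against 43%). It gives up about 2 points if there is no order effect.

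The split probabilities are exact under simple randomisation. The power figures depend on the assumed SD of differences and order effect. The documents give neither, so the size of the gain in this trial is unknown.

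**What to change.** First state whether each subject uses both treatments. If so:

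- **Protocol IV.C:** state that the order of Treatment 1 and Treatment 2 is counterbalanced from a pre-generated blocked list, 5:4 in 9 subjects.
- **SAP, Hypotheses 1 and 2:** replace the unpaired tests with a two-period crossover analysis. Estimate Treatment 1 minus Treatment 2 as the average of the two sequence-specific mean within-subject differences. Test it by comparing each subject's first-period minus second-period difference between the two sequences, by two-sample t-test or rank sum. Say explicitly that Treatment 1 minus Treatment 2 differences are not to be compared between sequences, since that tests the period effect.

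The cost is an order list, a short SAP change, one degree of freedom and about 1% of variance at 5:4. No extra subjects or visits are needed.

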## Statistical Power and Design

### Data Analysis

Functional measure and subjective measure data will be gathered and evaluated carefully by study team members without conflicts of interest to determine the distribution of all scores in the population studied and the variability of scores within and between the two study groups.

#### Evaluating the efficacy of the *Semi-Autonomous Myoelectric Control Algorithm*:

**Hypothesis 1 (primary):** We hypothesize that use of *Semi-Autonomous Myoelectric Control Algorithm* will improve dexterity relative to the standard-of-care prosthetic treatment. To validate this hypothesis, we will compare the two treatments (Treatment 1 vs. 2) during a single laboratory-based session using a task involving the transfer of a fragile object, recording the transfer success rate. We will use an Anderson-Darling test to check for normality. If the sample is normally distributed, we will use a two-sample Student's t-test to compare Treatment 1 and 2. If the sample is not normally distributed, we will use a Wilcoxon Rank Sum test to compare Treatment 1 and 2. If the hypothesis is correct, then we expect Treatment 1 (the *Semi-Autonomous Myoelectric Control Algorithm*) to show a significantly higher transfer success rate than Treatment 2.

**Hypothesis 2 (secondary):** We hypothesize that use of *Semi-Autonomous Myoelectric Control* will also provide improved assistance with prolonged gross motor movements. To validate this hypothesis, we will compare the two treatments (Treatment 1 vs. 2) during a single laboratory-based session using a task involving holding an object in the air for 2 minutes and recording the number of times the object is dropped. We will use an Anderson-Darling test to check for normality. If the sample is normally distributed, we will use a two-sample Student's t-test to compare Treatment 1 and 2. If the sample is not normally distributed, we will use a Wilcoxon Rank Sum test to compare Treatment 1 and 2. If the hypothesis is correct, then we expect Treatment 1 (the *Semi-Autonomous Myoelectric Control Algorithm*) to show a significantly fewer drops than Treatment 2.

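### Does resting the primary dexterity claim on transfer success rate alone, with no measure of time, undermine Hypothesis 1?

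*SAP*

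**What the plan says.** The SAP section on evaluating the algorithm's efficacy puts the primary hypothesis in terms of a construct: the algorithm "will improve dexterity relative to the standard-of-care prosthetic treatment". The same paragraph makes the construct measurable. The two treatments are compared "using a task involving the transfer of a fragile object, recording the transfer success rate", and if the hypothesis is right Treatment 1 is expected "to show a significantly higher transfer success rate than Treatment 2". The Power Calculation section agrees: "The primary outcome measure, transfer success rate of the fragile object, was used to inform the power calculation".

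Hypothesis 2 is a separate, secondary question with its own task: "holding an object in the air for 2 minutes and recording the number of times the object is dropped". It is a count over a fixed period and carries no information on speed.

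Protocol section IV.A is broader: "Outcome measures include completion rate, time to completion and path efficiency metrics", together with arm, wrist and hand position. Section IV.F repeats the three performance metrics as the output of the MATLAB processing. In the SAP text available, neither hypothesis uses time or path efficiency.

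**The concern.** Care and speed can be exchanged in handling a fragile object. A subject who slows down may break fewer objects without controlling the hand any better. Hypothesis 1 puts no condition on time, and the text available sets no pace or limit for a transfer. A significant rise in success achieved by slower movement would then be reported as improved dexterity, and equal success at higher speed would count as no benefit. The protocol appears to hold the data that would settle both cases, because it lists time to completion among its outcomes. If all of that held, the main conclusion would claim more than its measurement supports, and a cheap remedy would have been overlooked.

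**Working it through.** **1. The plan's own figure.** Inputs from the SAP's Power Calculation: mean success 59.2%, SD 20.7%, a sample size "necessary to detect a 20% difference in success with 80% power", z-test with known SD, result 9 subjects. Alpha and sidedness are not stated; 0.05 two-sided is assumed.

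- n = (SD × (z for alpha + z for power) / difference)² = (20.7 × (1.960 + 0.842) / 20)² = 8.41, rounded up to 9.
- Power at n = 9: Φ(20 / (20.7/√9) − 1.960) = Φ(2.899 − 1.960) = 82.6%. At n = 8 it is 78.0%.
- If the 20% is read as relative, the difference is 0.20 × 59.2 = 11.84 points and n is 24, which does not match.

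The figure reproduces as 20 percentage points on success rate. Outcome, hypothesis and sizing all refer to the same measure. (Whether a one-sample z-test suits the two-sample comparison planned is a separate matter and has no bearing on the choice of endpoint.)

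**2. How much slowing would matter.** The target effect is 59.2% to 79.2%, a ratio of 79.2 / 59.2 = 1.338. Successful transfers per unit time change by 1.338 divided by the ratio of time per attempt:

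| Time per attempt, Treatment 1 / Treatment 2 | Successful transfers per unit time, ratio |
|---|---|
| 1.0 | 1.34 |
| 1.2 | 1.11 |
| 1.338 | 1.00 |
| 1.5 | 0.89 |
| 2.0 | 0.67 |

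The break-even is a slowdown of about 34%. The time ratios are assumed, since the documents contain no transfer times. Throughput is also not an outcome in either document.

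**3. Is time recorded for this task?** The protocol is a general one for a laboratory's work on myoelectric controllers, with an estimated 60 subjects against the SAP's 9. It mentions neither a fragile-object transfer nor the semi-autonomous algorithm. Section IV.A refers to tasks without listing any. The one test goal that section IV.C spells out is matching hand postures shown on a screen, where completion, time and path efficiency all apply naturally. That section also mentions handling physical objects, so timing of transfers is possible, but no passage establishes it. Nor does any passage equate the protocol's completion rate with the SAP's transfer success rate.

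**4. Is pacing really absent?** Part of the SAP ahead of its Statistical Power and Design heading was not in the text available. A time limit or pace could be set there, so its absence cannot be asserted. The SAP's Data Analysis paragraph also covers functional and subjective measures in general, which is wider than the two hypotheses, so it is not safe to say that time has no place in the SAP.

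**5. Would adding time resolve the matter?** As a secondary outcome it leaves n at 9 and the primary result unchanged. If time were only reported beside success, a slower but more successful result could still be called improved dexterity. Mean time over all transfers is also hard to read. With success probability p, it equals p × t_s + (1 − p) × t_f, where t_s and t_f are the mean times of successful and failed attempts. Moving p from 0.592 to 0.792 changes the mean by 0.200 × (t_s − t_f) even if nobody moves faster or slower. If failures end early, mean time rises simply because success improved. Making time a required co-primary would be a different trial: with an assumed 80% power for time and independence, joint power at n = 9 is 0.826 × 0.80 = 66%.

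**The case for a change.** The strongest case for the concern is that dexterity is a broader word than transfer success, that the decision rule is silent on speed, and that the protocol lists a time metric which the available hypotheses do not use. Specifying a time analysis in advance would also prevent a later choice to show time only if it looked favourable, at no cost in sample size.

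Parts of this stand. The success rate does not measure speed, and a report that said transfer success rather than dexterity would be more exact. The possibility of a trade-off cannot be excluded from the documents.

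That does not make the plan wrong. Every single endpoint leaves something out: a success measure omits speed, and a speed measure omits breakage. Naming one outcome in advance and saying what result would support the hypothesis is ordinary good practice. That a gain on an unchosen outcome would be missed is true of any trial with one primary.

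**Conclusion.** The concern does not hold. The SAP defines its dexterity test as the fragile-object transfer success rate, prespecifies it as the only primary outcome and sizes the study on it. A reader can see exactly what a positive result means. Wanting a speed measure as well is a preference about endpoints, not an error in the analysis.

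The size of any effect on the conclusion cannot be obtained from the documents. The only figure available is the 34% break-even, which depends on reading the target as 20 percentage points and on a throughput measure from outside the plan.

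This conclusion covers the choice of endpoint only. It rests on three points about the text: time to completion is not tied to this task, the absence of pacing cannot be confirmed, and nothing points to a speed–success trade-off. If the study's task instructions showed that transfers are unpaced and that subjects slow down under Treatment 1, the interpretation of a positive result would deserve a caveat. The primary comparison would still be a comparison of success rates.

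### The SAP's claim of more than 80% power with 9 subjects comes from a one-sample z-test and does not hold for the two-sample t-test it names for the primary outcome

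*SAP*

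**What the plan says.** In the SAP's section on evaluating efficacy, both the primary outcome (transfer success rate for a fragile object) and the secondary outcome (number of drops while holding an object for 2 minutes) get the same analysis. After an Anderson-Darling check: "If the sample is normally distributed, we will use a two-sample Student's t-test to compare Treatment 1 and 2". Otherwise: "If the sample is not normally distributed, we will use a Wilcoxon Rank Sum test to compare Treatment 1 and 2". Both tests assume two independent samples.

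The SAP's Power Calculation starts from a published mean and SD ("We used an average success rate of" 59.2% ± 20.7%) and then uses a different test: "We selected a z-test for normally distributed data with a known standard deviation". The aim is the "number of subjects necessary to detect a 20% difference in success with 80% power". The result is that "a sample size of 9 subjects will achieve a power greater than 80" per cent. Alpha, sidedness and whether 9 is a total or a group size are not stated.

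The design has to be inferred from scattered wording:

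- The SAP's Data Analysis paragraph refers to "the variability of scores within and between the two study groups", which suggests parallel groups.
- Its hypotheses say "we will compare the two treatments (Treatment 1 vs. 2) during a single laboratory-based session", which fits either design.
- Protocol section IV.C says that each subject meets the controller versions in random order, which suggests paired data.

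**The concern.** A power figure describes one test applied to one design. Here the figure comes from one test and the planned analysis is another, and nothing in the available text connects them. The Power Calculation is the only justification of sample size in the documents, and it concerns the primary outcome.

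Two things are at stake. First, if the named t-test has much less than 80% power for the stated effect, a non-significant result says far less about absence of benefit than a reader of the SAP would think. Second, if each subject supplies a score under both treatments, the unpaired tests ignore the pairing. With positive within-subject correlation the consequence is mainly lost power, not extra false positives.

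**Working it through.** **Inputs.** From the SAP's Power Calculation: SD 20.7, difference 20%, target power 80%, 9 subjects, mean 59.2%. Assumed: alpha 0.05. The main figures are two-sided; one-sided figures at 0.05 are in brackets because the hypotheses are directional. The within-subject correlation ρ is not given, so a range is shown.

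**Step 1: reproduce the 9.** One-sample z-test: n = ((z for alpha + z for power) × SD / difference)². Two-sided, 20 points: ((1.960 + 0.842) × 20.7 / 20)² = 8.41, so 9. Power is 82.6% at n = 9 and 78.0% at n = 8. A two-group z-test doubles this, per group. A relative 20% is 0.20 × 59.2 = 11.84 points.

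| Version | 20 points, two-sided | 20 points, one-sided | 11.84 points, two-sided | 11.84 points, one-sided |
|---|---|---|---|---|
| One-sample z, n | 8.41 → **9** | 6.62 → 7 | 23.99 → 24 | 18.90 → 19 |
| Two-group z, n per group | 16.82 → 17 | 13.25 → 14 | 47.98 → 48 | 37.80 → 38 |

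At alpha 0.05, only the one-sample, two-sided, 20-point version gives 9. (One-sided 0.025 is the same calculation.) The arithmetic is right for that test. That the test is one-sample is inferred from this match; the SAP does not say so.

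**Step 2: power of the named two-sample t-test.** Noncentral t with n₁ + n₂ − 2 degrees of freedom and noncentrality 20 / (20.7 × √(1/n₁ + 1/n₂)).

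- 9 per group: 20 / (20.7 × √(2/9)) = 2.05 on 16 df; power 48.7% (62.4%).
- 9 in total, 4 and 5: 20 / (20.7 × √0.45) = 1.44 on 7 df; power 23.9% (36.6%).
- 9 subjects under both treatments, analysed as unpaired (simulated bivariate normal scores): about 49% for ρ from 0 to 0.7 (62% rising to 70%). At ρ = 0.95 it is still only 51% (78%).

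The exact rank-sum test gives 43% (59%) with 9 per group and 17% (27%) with 4 and 5.

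The difference detectable with 80% power by the named t-test is 29.1 points (25.4) with 9 per group and 45.4 points (38.4) with 4 and 5. If 59.2% is the comparator's mean, 59.2 + 45.4 = 104.6, which is beyond 100%.

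**Step 3: if the data are paired.** SD of the difference = 20.7 × √(2(1 − ρ)). Paired t-test: 8 df, noncentrality 20 × √9 / SD of the difference.

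| ρ | Paired t, n = 9: two-sided (one-sided) | Unpaired t on the same pairs: two-sided (one-sided) | Type I error of unpaired t: two-sided (one-sided) |
|---|---|---|---|
| 0 | 44% (59%) | 49% (62%) | 5.0% (5.0%) |
| 0.3 | 58% (72%) | 49% (65%) | 2.3% (2.7%) |
| 0.5 | 72% (84%) | 49% (67%) | 1.0% (1.4%) |
| 0.7 | 90% (96%) | 49% (70%) | 0.2% (0.4%) |

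The paired t-test reaches 80% with 9 subjects when ρ is about 0.59 (0.44) or more, that is, when the SD of the difference is at most 18.7 (22.0). The SAP's 20.7 accompanies a mean success rate, so it reads as the SD of a level and not of a difference.

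**Step 4: if a fixed benchmark was meant.** A one-sample t-test with 9 subjects has 72% (84%) power. The SAP plans no comparison with a fixed value.

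No figure is possible for Hypothesis 2, because the documents give no drop counts.

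**The case against.** The strongest objection is that the part of the SAP before its statistical section was not available and may describe the design. The design cues that can be read are weak. The protocol covers a general programme of about 60 subjects; its sentence on random order is followed by one about on-screen hand postures, not the two SAP tasks. The SAP's mention of two groups might even mean able-bodied and limb-deficient subjects, both of whom the protocol admits. So a contradiction between protocol and SAP on design is not proven, and the case for changing the tests is conditional. This stands, and it is why the fix has two branches. It does not rescue the power claim: a design description could settle which test is appropriate, but it could not give a two-sample t-test the power of a one-sample z-test.

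It can also be said that alpha, sidedness, ρ and the 4 and 5 split are assumptions. They are, and ranges are shown; the named t-test stays below 80% throughout those ranges.

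Finally, the harm is limited. False positives do not increase with positive correlation, the tests are appropriate if the groups are parallel, and 9 subjects may suffice with a paired test and high ρ. That is fair, but the power statement for the primary outcome is still wrong as written.

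**Conclusion.** The concern holds. The SAP's statement of more than 80% power does not belong to its primary t-test. At SD 20.7 per condition, 20 points and alpha 0.05, that test has 49% two-sided power (62% one-sided) with 9 per group, 24% (37%) with 9 in total, and about 49% (62 to 70%) with 9 pairs and ρ from 0 to 0.7. Confidence is high for this mismatch because it does not depend on which design was meant.

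Whether the tests themselves are wrong depends on the design. If the data are paired, both named tests should change; at ρ = 0.5, for example, the planned t-test has 49% power where a paired t-test on the same 9 subjects has 72%. If the groups are parallel, the tests fit and only the power statement is in error. The point should be corrected before analysis.

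**What to change.** State the design explicitly, and make protocol section IV.C and the SAP's Data Analysis, hypothesis and Power Calculation text agree with it.

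- **Each subject tested under both treatments.** For both hypotheses, replace the tests with a paired t-test or Wilcoxon signed-rank test on within-subject differences, and check normality on those differences. Report the mean difference with its 95% confidence interval. If the SAP's two groups are in fact the two treatments, call them treatment conditions. Restate the power of 9 subjects from an explicit SD of the difference, alpha and sidedness; if that SD is 20.7, power is 72% two-sided or 84% one-sided at 0.05.
- **Parallel groups.** Keep the tests, give the actual group sizes, and restate power for them: 49% two-sided or 62% one-sided with 9 per group; 24% or 37% with 9 in total.

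The cost is SAP wording; data and subjects are unchanged, and this point does not call for more of either. There are two downsides. The restated power may look less favourable. If the data are paired and ρ is below about 0.12 (0.09 one-sided), the paired t-test is slightly weaker than the planned one: at ρ = 0, 44% against 49% two-sided, or 59% against 62% one-sided. Likewise signed-rank against rank-sum at ρ = 0 is 38% against 43% two-sided.
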